| Patient Population | 
1. Adult women with known or suspected gynecological cancers who have had or are scheduled to undergo a hysterectomy and/or salpingo-oophorectomy. N=40
 
2. Normal controls: Women with no imaging evidence of gynecological cancer, who are undergoing hysterectomy and/or salpingo-oophorectomy. N=12 (includes up to 6 Dosimetry subjects)
 
a. Dosimetry : Women with or without suspected gynecological cancer.
 |
| Accrual Objective | 52 women |
| Study Design | Phase 2, single-center, open-label study |
| Study Duration | The estimated accrual period is over 3 years. |
| Primary Objective | 
The purpose of this research is to evaluate whether a novel imaging approach using PSMA-based ¹⁸F-DCFPyL PET and MR imaging can:
 
 1. Document the normal distribution of PSMA in the abdomen and pelvis on PET imaging. 2. Document the normal appearance of the fallopian tubes and ovaries on high resolution MR imaging 3. Accurately determine the presence or absence of cancer 4. Accurately identify the distribution of cancer |
| Specific Aims | 
 1. To establish the biodistribution and radiodosimetry of PSMA-based ¹⁸F-DCFPyL on PET imaging in normal female controls and in females with known or suspected cancer. 2. To determine the ability of PSMA-based ¹⁸F-DCFPyL PET and MR imaging to detect cancer in women with known or suspected gynecologic malignancy and differentiating cancerous tissue from non-cancerous tissue. The performance of PSMA-based ¹⁸F-DCFPyL PET imaging in the detection and localization of cancerous and non-cancerous tissue will be compared to the final surgical pathology reports and to the histological and immunostaining for PSMA positive cancerous tissue on pathology. 3. To determine the most accurate approach in assessing disease burden and location, assessment of tumor burden on both the PSMA-based ¹⁸F-DCFPyL PET and MR imaging together, and then each modality separately will be performed and sensitivity, specificity, and accuracy values will be calculated. |
| Inclusion Criteria | 
 • Women with no imaging evidence of cancer • Women with suspected or documented gynecological cancer and previously underwent or scheduled to undergo a hysterectomy and/or salpingo-oophorectomy • No contraindications for MR or PET imaging. • Greater than or equal to 18 years |
| Exclusion Criteria | 
 • Women that are pregnant or breast feeding. • Age <18 |

| | |
|----------------------------|--|
| | 
 • Severe kidney dysfunction (GFR <30 mL/min/1.73m²) |
| Treatment Description | ¹⁸ F-DCFPyL whole body PET/CT or PET/MR scan |
| Study Procedures | 
 • ¹⁸F-DCFPyL whole body PET/CT imaging for dosimetry studies; PET/MR scan to achieve other aims • Review of relevant imaging and medical record information |
| Statistical Considerations | 
There are no formal hypothesis tests planned.
 
Our primary goals are to:
 
 1. Record the normal biodistribution and radiodosimetry of PSMA in the body 2. Record the frequency the normal fallopian tubes and ovarian are seen on high resolution MR imaging. 3. Record the distribution of PSMA in cancer tissue 4. Estimate the frequency with which PSMA PET and MR imaging and final IHC staining disagree in their classifications of presence of disease. We will classify each data point as either an agreement or disagreement between imaging findings and IHC staining. The proportion of disagreements across all time points will be estimated with an intercept-only GEE regression model that accounts for correlation among measures from the same patient. This proportion will be reported with a 95% confidence interval. The lower bound of this confidence interval will be used to help us decide whether this approach is worthy of future study. Based on this pilot study we plan to pursue further evaluation in larger more appropriately powered studies if the lower bound of the confidence interval excludes 20%, which is chosen as a guideline to determine whether the method shows promise. |

SCHEMATIC OF STUDY DESIGN

Subject Populations

1.0 PROJECT SUMMARY:

The purpose of our proposal is to use PSMA PET and multi-parametric MR imaging, to detect the presence of gynecological cancer cells in the body. Imaging evaluation would include the appearance of normal ovaries/fallopian tubes, and cancerous tissue on different MR sequences and the distribution of PSMA in normal and pathological tissues on PET images. To determine the accuracy of the PSMA PET imaging localization in malignant tissues, PSMA staining of surgical pathology specimens will be used as the reference standard.

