10.0 STATISTICAL CONSIDERATIONS

The goals of this study are to 1) record the normal distribution of PSMA in the body, 2) record the frequency that the normal fallopian tubes and ovarian are seen on high resolution MR imaging, 3) record the distribution of PSMA in cancer tissue, and 4) estimate the sensitivity, specificity, and accuracy of PSMA PET and MR imaging.

12 healthy controls and 40 subjects with known gynecologic cancer will be enrolled in this pilot study. With final IHC staining as the “gold standard” in detection of cancer, we will estimate the sensitivity, specificity, and accuracy of PSMA PET and MR imaging. The sample size was chosen based on logistical and financial considerations. The table below shows the precision with which we will be able to estimate the sensitivity and specificity of PSMA PET and MR imaging.

| Sensitivity/Specificity | Width of 95% CI |
|-------------------------|-----------------|
| 65% | 31.1% |
| 70% | 29.9% |
| 72.5% | 29.3% |
| 75% | 28.5% |
| 77.5% | 27.7% |
| 80% | 26.5% |
| 82.5% | 25.5% |
| 85% | 24.1% |

Based on this pilot study, we plan to pursue further evaluation in larger, more appropriately powered studies if sensitivity and specificity are at least 80%.

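### The synopsis decides on further study from the lower confidence bound of the disagreement rate, which cannot show low disagreement, and Section 10 gives a different rule

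*Combined protocol and SAP*

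**What the plan says.** Synopsis, Statistical Considerations, item 4:

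- Unit: "We will classify each data point as either an agreement or disagreement between imaging findings and IHC staining".
- Estimate: "The proportion of disagreements across all time points will be estimated with an intercept-only GEE regression model", a model that "accounts for correlation among measures from the same patient". It is reported with a 95% confidence interval.
- Use: "The lower bound of this confidence interval will be used to help us decide whether this approach is worthy of future study".
- Threshold: "further evaluation in larger more appropriately powered studies if the lower bound of the confidence interval excludes 20" per cent, a figure "chosen as a guideline to determine whether the method shows promise".

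The same synopsis entry says that no formal hypothesis tests are planned.

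Section 10.0 does not mention the disagreement proportion, the GEE model or a confidence bound for the decision. Its fourth goal is "4) estimate the sensitivity, specificity, and accuracy of PSMA PET and MR imaging", with IHC again as the reference. It plans "larger, more appropriately powered studies if sensitivity and specificity are at least 80" per cent.

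Neither place refers to the other or says which rule takes precedence.

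**The concern.** Disagreement is a failure rate. Evidence that a failure rate is low comes from the upper limit of its interval; the lower limit can only show that the rate is high. The synopsis uses the lower limit and does not say on which side of 20% it must fall. One reading rewards poor imaging. The other passes methods whose observed disagreement is well above 20%.

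Section 10 then decides the same question by another measure, with no interval. Unless one rule is fixed before results are seen, the direction of the synopsis rule and the choice between the two rules can both be settled afterwards.

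The unit is also open. The synopsis pools over time points, but Section 5.0 gives each woman one research visit. Dosimetry subjects do have five PET scans within that visit, but those scans serve Aim 1. Stained surgical sites (Section 5.0) or separate readings by modality (Section 3.0, aim 3) could be the repeated measure. The documents do not say.

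**Working it through.** **Inputs.** From the documents: 95% interval, 20% and 80% thresholds, 40 cancer patients and 12 controls (Section 10). Not in the documents: the number of data points per woman, their correlation, and the split of IHC-positive and IHC-negative points. Steps 2, 3 and 6 assume one independent point per woman.

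**1. The plan's own figures.** For x events in n, the exact (Clopper–Pearson) limits are the 2.5% quantile of Beta(x, n−x+1) and the 97.5% quantile of Beta(x+1, n−x). With n = 40 these reproduce all eight widths in the Section 10 table to within about 0.1 point. At 80%, 32/40 gives 64.4–90.9%, a width of 26.6 against the stated 26.5. The table is not at fault, and exact limits at n = 40 are a fair basis for what follows.

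**2. Cut-offs for the disagreement rate.**

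| Rule | n = 40 | n = 52 |
|---|---|---|
| Lower bound above 20%: fewest disagreements for go | 14 (35.0%; 20.6–51.7%) | 17 (32.7%; 20.3–47.1%) |
| Lower bound below 20%: most disagreements for go | 13 (32.5%; 18.6–49.1%) | 16 (30.8%; 18.7–45.1%) |
| Upper bound below 20%: most disagreements for go | 2 (5.0%; 0.6–16.9%) | 4 (7.7%; 2.1–18.5%) |

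Perfect agreement, 0/40 (0–8.8%) or 0/52 (0–6.8%), is a no-go on the first row. Wilson limits move the n = 40 cut-offs by one (13, 12 and 3) and leave those at n = 52 unchanged.

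**3. Probability of go, n = 40 (binomial tails).**

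| True disagreement | Lower bound above 20%: P(X ≥ 14) | Lower bound below 20%: P(X ≤ 13) | Upper bound below 20%: P(X ≤ 2) |
|---|---|---|---|
| 5% | <0.0001 | >0.999 | 0.68 |
| 10% | <0.0001 | >0.999 | 0.22 |
| 20% | 0.02 | 0.98 | 0.008 |
| 30% | 0.30 | 0.70 | 0.0001 |
| 40% | 0.79 | 0.21 | <0.0001 |
| 50% | 0.98 | 0.02 | <0.0001 |

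The first rule becomes more likely to say go as imaging gets worse. At 30% true disagreement and n = 52, the second rule gives P(X ≤ 16) = 0.61.

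**4. Several correlated points per woman.** Take 80 to 200 points, a design effect of 1 to 3, effective n = points ÷ design effect, and a logit-scale Wald interval. On the below-20% reading, the largest observed disagreement that still passes is 25.5% (200 points, design effect 1) to 30.6% (160 points, design effect 3) while the effective n is at least 53. It rises to 35.0% with 80 points and design effect 3. The cut-offs move, but the fault remains.

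**5. The synopsis rule against Section 10.** Let π be the share of IHC-positive points. On the same points, pooled,

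disagreement = π(1 − sensitivity) + (1 − π)(1 − specificity).

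If sensitivity and specificity are both at least 80%, this is at most 0.20π + 0.20(1 − π) = 20%. A lower bound does not exceed its estimate, so it cannot be above 20%. On the above-20% reading the two rules can never both say go. On the below-20% reading, meeting Section 10 implies a synopsis go, but not the reverse: 13/40 disagreements passes the synopsis with accuracy 27/40 = 67.5%, so sensitivity and specificity cannot both be 80%.

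This holds for a pooled proportion. The synopsis names no working correlation. A structure that weights women rather than points can move the GEE estimate away from the pooled proportion, and both rules could then say go.

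**6. Example (assumed 40 positive, 12 negative).** With 32/40 and 10/12 correct, sensitivity is 80% and specificity 83.3%, which just meets Section 10. Disagreements are 8 + 2 = 10 of 52 (19.2%; 9.6–32.5%). That is a go under Section 10, a no-go on the above-20% reading and a go on the below-20% reading.

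**The case against.** The strongest reply is that little hangs on the rule. No test is planned, 20% is a guideline, and the proportion and its full interval will be reported whatever the rule says. Only the decision on a later study is affected. That is correct, and no type I error claim is made here. But this is the synopsis's only go criterion, and separating a promising method from an unpromising one is its stated purpose.

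Second, it may be a slip: 20% and 80% are complements, and agreement may have been meant. That is plausible, but item 4 defines disagreement explicitly and nothing in the documents corrects it.

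Third, on the below-20% reading the rules are nested rather than opposed, and a lenient screen is a legitimate choice for a pilot. This narrows the conflict to one reading. It does not settle which reading is meant, and it fits poorly with a bound that has to exclude 20%.

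Fourth, the n = 52 and 40/12 figures are weakly supported. Section 5.0 assigns Aims 2 and 3 to the 40 patients. Up to 6 of the 12 controls are dosimetry subjects, for whom Section 4.0 lists no surgery criterion, and patients with suspected cancer need not all be IHC-positive. This objection stands: those figures are illustrations only. The conclusion needs only the n = 40 results and the argument about direction.

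**Conclusion.** The concern holds, and the rule should be corrected before results are seen. As worded, the synopsis criterion either requires evidence of more than 20% disagreement (first go at 14/40, with 0/40 a no-go) or passes up to 13/40, with a 70% chance of go at 30% true disagreement. Neither version shows that disagreement is low. Section 10 gives a second, different criterion, and the documents do not say which one governs.

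The wrong side of the interval and the lack of reconciliation need no assumption about sample size or correlation. The exact cut-offs assume one independent point per woman. The statement that the above-20% reading and Section 10 cannot both say go assumes pooled estimates on the same data points.

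**What to change.** State one go criterion, identically, in the synopsis and in Section 10. There are two ways:

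1. **Upper bound.** Go if the upper limit of the 95% interval for the proportion of disagreements is below 20% (equivalently, the lower limit for agreement is above 80%). Make the Section 10 sensitivity and specificity rule descriptive.
2. **Section 10 rule.** Go if sensitivity and specificity are both at least 80%. Make the disagreement proportion descriptive.

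In either case replace the reference to time points with the unit the sponsor intends, for example stained site within patient, and name the GEE working correlation if the model is kept.

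The edit is to wording only, but the options differ in strictness. Option 1 allows at most 2/40 or 4/52 disagreements. Its probability of go is 68% (n = 40) or 88% (n = 52) at 5% true disagreement, and 22% or 40% at 10%. Option 2 is easier to meet but uses no interval. With the assumed 40/12 split, P(at least 32 of 40) × P(at least 10 of 12) is 0.985 × 0.889 = 88% if both true values are 90%, 0.593 × 0.558 = 33% if both are 80%, and 0.300 × 0.391 = 12% if both are 75%. The choice is the sponsor's; the requirement is a single rule with a stated direction and unit.

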2.0 INTRODUCTION

Background:

The detection and distribution of cancer prior to definitive treatment is the standard of care currently [1]. Imaging plays a crucial role in this process of identifying possible areas of tumor prior to initiation of treatment [2]. Currently, imaging techniques used in clinical practice to visualize cancer mainly involve basic cross sectional anatomical imaging with or without intravenous contrast administration. These imaging techniques are limited by only providing “anatomical” information, and the diagnosis of cancer and normal tissue is partly determined by the location of the tissue. Imaging contrast agents can help visualize abnormalities, but currently cannot differentiate between malignant, inflammatory or fibrotic (scar) tissues. There have been major research advancements in functional imaging, which allow the physician to determine better what type of tissue is present in an anatomical location. Advanced PET and MR imaging techniques can evaluate the chemical composition and metabolic activity of different tissues [3, 4]. MR imaging can depict the composition of tissue (water, fat, blood and cellular) by imaging the molecules in the human body. PET imaging can depict whether or not tissue is metabolically active by imaging the injectable metabolic tracer which is taken up by different area or tissue types in the body. Knowing both the composition of the tissue and the metabolic fingerprint can help differentiate more accurately between non-cancerous and cancerous tissue types [5]. This in turns allows for more accurate cancer screening and pre-treatment staging, both which have been shown to improve outcomes in gynecologic cancer patients [1, 6]. ¹⁸F-FDG PET imaging is widely used for cancer detection and staging, but can be limited due to nonspecific uptake at sites of inflammation. A more specific PET imaging agent for more specific tumor detection, particularly in gynecologic malignancy, would help meet an unmet clinical need.

PSMA, also known as folate hydrolase 1 andglutamate carboxypeptidase II, is an enzyme associated with prostate cancer but has been also found to be expressed in the tumor neovasculature of many different types of non-prostate cancer tumors [7, 8]. The PSMA molecule can be bound to a PET radionuclide as an imaging agent, specifically, ¹⁸F-DCFPyL, and this agent can be detected non-invasively using PET imaging. PSMA-based ¹⁸F-DCFPyL PET demonstrates very high tumor-to-background ratio when studied in other tumors, including prostate tumors [9]. In prostate cancer, the agent has been shown to improve detection of prostate tumors and the amount of tumor present throughout the body (tumor burden). Similar high tumor-to-background uptake of PSMA-based PET imaging has been demonstrated targeting the tumor

neovasculature of non-prostate solid tumors (example: renal cell carcinoma and lung) with potential improved tumor specificity [10, 11]. There is growing evidence in the literature which demonstrates that correctly identifying the tumor burden allows the treating physician to tailor the treatment more specifically to the individual patient to assure all the cancer cells are treated [12]. Recently, an immunohistologic pathology study demonstrated PSMA is highly and specifically expressed in the tumor vasculature of ovarian and uterine tumor specimens [9]. This makes exploring PSMA as a potential functional imaging agent for ovarian cancer very intriguing.

MR imaging is a highly sensitive and specific imaging modality that can be used for gynecologic cancers. MR images can be obtained in conjunction with PSMA PET, adding additional anatomic and multi-parametric MRI information without the need for a second imaging appointment. Emerging data demonstrates that the inclusion of functional MR sequences, specifically diffusion weighted sequences, increases the sensitive and specificity of MR imaging in the detection of tumors, including metastatic cancer deposits [3, 5].

The overarching goals of this pilot study are to determine if imaging can depict PSMA ¹⁸F-DCFPyL uptake in gynecological cancers seen on MR imaging, and to correlate both the PSMA PET and MR imaging with histological and immunologic staining of resected tumor specimens in women undergoing the standard of care surgical treatment of their gynecological cancers. If it is possible to see PSMA on acquired images, PSMA ¹⁸F-DCFPyL could potentially be used for both screening and pre-treatment assessment of women with gynecologic cancers with improved sensitivity and specificity.

3.0 STUDY AIMS/STUDY OBJECTIVES

The primary outcome of this research is to evaluate whether a novel imaging approach using PSMA-based ¹⁸F-DCFPyL PET and MR imaging can accurately determine the presence or absence of cancer, the accurate distribution of cancer and the normal biodistribution of PSMA in the abdomen and pelvis on PET imaging. The reference standard for the PSMA localization in cancerous tissue will be histologic and immunologic correlation on the pathologic specimens obtained at the time of standard of care surgical resection for treatment of the gynecological cancer. Specific aims for this research include the following:

1. To establish the biodistribution and radiodosimetry of PSMA-based ¹⁸F-DCFPyL on PET imaging in normal female controls and in females with known or suspected cancer.
2. To determine the sensitivity, specificity, and accuracy values of PSMA-based ¹⁸F-DCFPyL PET and MR imaging in the detection of cancer in women with known or suspected gynecologic malignancy and differentiating cancerous tissue from non-cancerous tissue. The performance of PSMA-based ¹⁸F-DCFPyL PET imaging in the detection and localization of cancerous and non-cancerous tissue will be compared to the final surgical pathology reports and to the histological and immunostaining for PSMA positive cancerous tissue on pathology.
3. To determine the most accurate approach in assessing disease burden and location, assessment of tumor burden on both the PSMA-based ¹⁸F-DCFPyL PET and MR imaging

together, and then each modality separately will be performed and sensitivity, specificity, and accuracy values will be calculated.

4.0 RESEARCH DESIGN AND METHODS:

Subject population

Fifty-two subjects will be enrolled in this research, 12 healthy controls and 40 patients with known or suspected gynecologic cancer. Up to 6 subjects will be used for the dosimetry portion. Eligibility requirements include the following:

Inclusion Criteria for healthy female controls N=12 (includes up to 6 Dosimetry subjects)

1. Women with no suspected gynecological cancer
2. No contraindications for MR or PET imaging
3. Greater than or equal to 18 years of age
4. Scheduled to undergo a hysterectomy and/or salpingo-oophorectomy

Inclusion Criteria for female controls (Dosimetry)

1. Women with or without suspected gynecological cancer
2. No contraindications for MR or PET imaging
3. Greater than or equal to 18 years of age

Inclusion Criteria for gynecologic cancer patients N=40

1. Women with known or suspected gynecological cancer
2. No contraindications for MR or PET imaging.
3. Greater than or equal to 18 years
4. Have had or are scheduled to undergo a hysterectomy and/or salpingo-oophorectomy

Exclusion Criteria

1. Women that are pregnant or breast-feeding.
2. Age <18
3. Inability to provide informed consent on their own behalf
4. Severe kidney dysfunction (GFR <30 mL/min/1.73m²)

Subject identification and recruitment

Healthy controls will be recruited from UWHC OB/Gyn and Women's Health and PATHS clinics through referrals and from posted flyers. Healthy controls may also be recruited from the Department of Radiology Volunteer Database (2017-0004). Potential subjects will either be introduced to the research by someone involved in their care or they will be required to contact

the study team by phone or email. Those interested in participating will be scheduled for an initial visit to learn more about participation and to complete the informed consent process.

Gynecologic Oncology staff will identify cancer patients who meet the eligibility criteria and will introduce them to this research opportunity. Those interested will be referred to a study team member who will review the purpose of the research as well as details about participation.

Informed Consent and Subject Information

The consent process will occur either on a day prior to or on the day of but prior to the administration of research procedures. During the COVID-19 pandemic, consent procedures will be conducted by phone to minimize face-to-face contact subjects have with the research team. An encrypted copy of the consent form will be mailed or emailed to subjects prior to the scheduled consent phone call. A study team member will call potential subjects at the scheduled time to review the information in the consent form including study procedures, risks associated with participation, alternatives to participation and whom to contact for additional information. Any questions will be addressed during the course of the phone call and subjects will be encouraged to contact the study team with any questions or concerns they might have at any time. Upon completion of the consent process, subjects will be asked to return a copy of the signed consent form by either scanning the entire document and email back to the study team member or taking a photo of the signature page and emailing a copy to the study team member.

Once institutional requirements are met, remote consenting will continue by obtaining electronic signature using the DocuSign software platform.

Prior to the start of any research procedures and all subjects will be reminded that participation is optional and they can change their mind at any time.

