5.0 STUDY PROCEDURES

Subjects will be asked to complete a single research visit that will include the administration of a PSMA PET/CT and/or PET/MR exam. Subjects participating in the PET/MR imaging studies will be screened for contraindications to MRI and MR contrast agents using the standard UWCHC MR Safety screening form. A urine pregnancy test will only be done for women with childbearing capacity that are unable to verify their non-pregnancy status by self-report.

Aim 1. Biodistribution and radiodosimetry of PSMA-based ¹⁸F-DCFPyL in normal female controls or cancer patients (Up to 6 subjects for non-dosimetry and 6 subjects for radiodosimetry (dosimetry))

The research visit is estimated to take 2-3 hours, which includes approximately 60-120 minutes of scanning time. Subjects will be asked to fast for 4 to 6 hours prior to the research visit and to stay well hydrated.

The remainder of the time will be preparatory for the scanning. An IV will be placed to allow injection of the PET tracer during the exams.

Dosimetry Subjects: A less than 9 mCi dose of ¹⁸F-DCFPyL radiotracer will be administered by slow IV push after subject has been positioned in the PET/CT scanner. The subject's imaging session will include multi-pass PET scans to allow for normal organ and tumor biodistribution for a total of 5 PET scans from the vertex of skull through mid-thigh. Initial low-dose CT will be followed by 4 PET scans (PET1 through PET4) lasting approximately 60 to 75 minutes (depending on the height of the patient). The subjects will be allowed to leave the table to void between the fourth and fifth (PET5) PET scans. The fifth PET/CT scan (PET5) is obtained with another low-dose CT scan to allow for CT attenuation correction followed by the PET scan starting at approximately 90 minutes after radiotracer administration to last up to approximately 30 minutes (again, depending on the height of the patient). If the PET/CT takes less than 120 minutes, the subject may undergo a PET/MR, as time allows.

Dosimetry Subjects Only - Blood Collection:

- Blood (5mL Purple top at each time point) will be collected at 3 time points, after the completion of the 2nd, 4th and 5th PET passes on the PET dosimetry PET/CT protocol. Blood will be collected for the first 3 subjects and as needed for the remaining 3 subjects.

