- Blood will be counted on a gamma counter after dilution to determine radioactivity on the same day as the scan. After radioactive decay overnight, blood will be disposed of as per routine biohazard.

Non-dosimetry subjects: An IV will be placed to allow injection of the PET tracer, MR gadolinium agent, and glucagon (if needed) during the exams. A less than 9 mCi dose of ¹⁸F-DCFPyL radiotracer will be administered by slow IV push outside the scanner, after which, the subject will be required to sit quietly for 60 minutes to allow for adequate biodistribution of the tracer. The subjects will then be placed in the PET/MR scanner and will remain in the scanner for up to 90 minutes. After which, the whole body (defined in this protocol as base-of-skull to mid-thigh) PET and MR images will be obtained to include images post-intravenous gadolinium contrast. Glucagon (0.5mg-1mg, IV) may be administered by IV prior to the MR imaging if excessive bowel movement is seen on initial images. Glucagon is known to diminish bowel motion and improve MR image quality.

Aims 2 & 3. Sensitivity, specificity, and accuracy values of PSMA-based ¹⁸F-DCFPyL PET and MR imaging and assessment of tumor burden (40 subjects with known or suspected gynecological cancer).

This research visit is estimated to take 2-3 hours. For subjects with gynecologic cancer, the subjects will be in the scanner for up to 90 minutes. The remainder of the time will be preparatory for the scanning. An IV will be placed to allow injection of the PET tracer, MR gadolinium agent, and glucagon (if needed) during the exams. Subjects will be asked to fast for 4 to 6 hours prior to the research visit and to stay well hydrated. There will be a 1-hour uptake period after IV administration of less than 9 mCi of ¹⁸F-DCFPyL radiotracer by slow IV push. After which, the whole body (defined in this protocol as base-of-skull to mid-thigh) PET and MR images will be obtained to include images post-intravenous gadolinium contrast. Glucagon (0.5mg-1mg, IV) may

be administered by IV prior to the MR imaging if excessive bowel movement is seen on initial images. Glucagon is known to diminish bowel motion and improve MR image quality.

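### Aim 3 asks which of three reads is most accurate, but no between-read difference is estimated, although PET and MR come from the same women

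*Combined protocol and SAP*

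**What the plan says.** Section 3.0, Aim 3, opens with "To determine the most accurate approach in assessing disease burden and location". The method that follows is to assess PET and MR "together, and then each modality separately will be performed and sensitivity, specificity, and accuracy values will be calculated". The synopsis repeats this under Specific Aims.

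Section 5.0 shows that the data are paired. It states "Subjects will be asked to complete a single research visit", and for Aims 2 and 3 PET and MR images are both obtained after a single tracer injection. The group is described as "assessment of tumor burden (40 subjects with known or suspected gynecological cancer".

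Section 10.0 lists four goals, none of which compares reads. Its precision table concerns one proportion at a time, and its rule for going on to a larger study is an absolute 80% for sensitivity and specificity. On sample size it says "The sample size was chosen based on logistical and financial considerations".

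The synopsis, under Statistical Considerations, states "There are no formal hypothesis tests planned". It plans one model that allows for correlated data: an intercept-only GEE for the proportion of imaging results that disagree with IHC staining.

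**The concern.** The aim asks which read is best; the analysis describes each read separately. The quantity that answers the aim is the within-woman difference between reads, and no section estimates it. Nor is there a discordance table or a rule for naming a best read.

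The intercept-only GEE does not fill the gap. It returns one overall disagreement proportion and has no term for the read, so it cannot say whether PET alone, MR alone or the combination does better.

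With only separate values in hand, a reader can do little more than pick the highest point estimate and look at overlapping intervals. Such intervals ignore the agreement between reads on the same women, which is the information that pairing supplies.

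**Working it through.** **1. The plan's own figure.** Section 10.0 gives full 95% interval widths from 31.1 points (at 65%) to 24.1 points (at 85%), without stating n. Exact (Clopper-Pearson) intervals with n = 40 give 31.1, 30.0, 29.3, 28.5, 27.6, 26.6, 25.4 and 24.1, all within 0.1 point of the table. So the table describes one read in 40 units. For example, 32/40 gives about 64% to 91% and 28/40 about 53% to 83%, which overlap widely.

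**2. Assumptions.** The documents give no expected difference and no discordance rate. I assume reads of 80% and 70% (d = 0.10), n = 40, and a discordant share ψ from 0.10 to 0.38. The lower end is the smallest ψ compatible with d = 0.10 (all discordance in one direction). The upper end is independence: 0.8 × 0.3 + 0.2 × 0.7 = 0.38.

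**3. Pairing ignored.** SE = √(0.8 × 0.2/40 + 0.7 × 0.3/40) = √(0.37/40) = 0.0962. The interval is 0.10 ± 1.96 × 0.0962, that is -8.9 to +28.9, width 37.7 points.

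**4. Pairing used.** SE = √((ψ − d²)/n), Wald interval:

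| ψ | Discordant pairs of 40 | SE | 95% CI (points) | Width | Narrower than 37.7 by |
|---|---|---|---|---|---|
| 0.10 | 4 v 0 | √(0.09/40) = 0.0474 | +0.7 to +19.3 | 18.6 | 51% |
| 0.15 | 5 v 1 | √(0.14/40) = 0.0592 | -1.6 to +21.6 | 23.2 | 38% |
| 0.20 | 6 v 2 | √(0.19/40) = 0.0689 | -3.5 to +23.5 | 27.0 | 28% |
| 0.30 | 8 v 4 | √(0.29/40) = 0.0851 | -6.7 to +26.7 | 33.4 | 11% |
| 0.38 | independence | √(0.37/40) = 0.0962 | -8.9 to +28.9 | 37.7 | 0% |

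Wald intervals are shaky with so few discordant pairs. In the first row the interval excludes zero, yet the exact two-sided McNemar p-value for 4 v 0 is 2 × 0.5⁴ = 0.125. For 5 v 1 it is 2 × (1 + 6)/64 = 0.22.

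**5. What 40 women can separate.** Exact McNemar power at the two-sided 5% level for a 10-point difference is 21%, 20%, 17% and 13% at ψ = 0.10, 0.15, 0.20 and 0.30. For 20 points it is 84% at ψ = 0.20 and 57% at 0.30. By the normal approximation, 80% power for 10 points needs 116, 155 or 234 pairs at ψ = 0.15, 0.20 or 0.30. These figures gauge resolution; they do not imply that a test should have been planned.

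**6. Denominators.** Scored per woman, n = 40 fits accuracy. Sensitivity uses only women with disease and specificity only those without, so 40 women known or suspected to have cancer cannot supply 40 to each. With 30 women, the exact single-read width at 80% rises from 26.6 to 30.9 points. The paired widths at ψ = 0.10, 0.15, 0.20 and 0.30 become 21.5, 26.8, 31.2 and 38.5, against √(0.37/30) × 3.92 = 43.5 points with pairing ignored. The documents do not fix whether the unit is the woman or the site.

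**The case against.** The strongest reply is that this is a descriptive pilot, sized on logistics and finance, with no tests planned and larger studies to follow. No stated decision depends on ranking the reads: the Section 10.0 rule is an absolute threshold, and the synopsis rule concerns disagreement with IHC. Separate values per read fit that scope. This stands as a limit on the consequence. It does not remove the gap, because an interval for a difference is estimation, and the synopsis already plans an interval for its disagreement proportion.

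A reader might infer that neglect of pairing is what stops the plan from ranking the reads. The documents do not support that. Sample size is the main limit: for a 10-point difference the paired intervals at 15% discordance and above still include zero.

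A reader might also infer that the plan specifies a faulty unpaired comparison, or disregards within-patient correlation throughout. It does neither. It specifies no comparison, so the 37.7-point width is only a yardstick, and the synopsis GEE does allow for correlation in its own analysis.

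Finally, one might want to name the combined read minus MR as the main contrast. Aim 3 ranks no contrast above another, so that would be a preference.

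**Conclusion.** The point holds as a mismatch between aim and analysis. Aim 3 seeks the most accurate of three reads, while the plan only calculates values read by read and leaves the paired difference unestimated.

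The gain from pairing cannot be fixed from the documents. For 80% v 70% with 40 women and Wald intervals, it runs from about half the interval width at 10% discordance to nothing at 38%. Patient-level sensitivity and specificity cannot both rest on 40 women, so their intervals should be expected to be wider than those shown.

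Reporting the difference would make the uncertainty of the comparison visible and usually smaller. It would not reliably rank reads about 10 points apart. At n = 40 only differences near 20 points with low discordance are likely to stand out. This is a worthwhile, low-cost improvement; it does not invalidate the descriptive results.

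**What to change.** In Aim 3 (Section 3.0 and the synopsis) and in Section 10.0:

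- Report the paired differences between reads (combined v PET, combined v MR, PET v MR) in sensitivity, specificity and accuracy, each with a 95% interval.
- State whether the unit is the woman or the site. Per woman, use a score-type or exact-type paired interval. Per site, use a patient-clustered bootstrap or a GEE with a term for the read.
- Show the discordant-pair table for each contrast, separately for diseased and non-diseased units.
- Word Aim 3 as exploratory estimation of the differences between reads.

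The three reads are already planned, so this adds no patients, scans or readings, only some lines of analysis text and code. The one practical condition is that, for a site-level analysis, all three reads are scored against the same list of sites in each woman. The documents do not describe such a scoring form, so it should be settled before reading starts.
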